8.4.4 Pharmacokinetic Analyses

Not applicable

8.4.5 Biomarker Analyses

The exploratory biomarker measurements of hsCRP and NT-proBNP will be summarized with descriptive statistics by treatment.

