1.3.3 Exploratory Objectives

Short-term:

- To assess the proportion of subjects achieving therapeutic glycemic response, defined as HbA1c < 7.0%, without any hypoglycemia at Week 52 achieved with saxagliptin, in co-administration with dapagliflozin, added to current background therapy with metformin, compared to glimepiride added to current background therapy with metformin.
- To assess the proportion of subjects achieving therapeutic glycemic response, defined as HbA1c < 7.0%, without any hypoglycemia and weight gain at Week 52 achieved with

saxagliptin, in co-administration with dapagliflozin, added to current background therapy with metformin, compared to glimepiride added to current background therapy with metformin.

- To assess mean change from baseline in FPG achieved with saxagliptin, in co-administration with dapagliflozin, added to current background therapy with metformin, compared to glimepiride added to current background therapy with metformin at Week 52.
- To assess change from baseline of metabolic measures (glucagon, C-peptide, pro-insulin, insulin, iHOMA2) at Week 52 achieved with saxagliptin, in co-administration with dapagliflozin, added to current background therapy with metformin, compared to glimepiride added to current background therapy with metformin.
- To assess change from baseline in average glucose values and postprandial glucose values measured by 6-point self-monitored blood glucose (SMBG) profiles at Week 52 achieved with saxagliptin, in co-administration with dapagliflozin, added to current background therapy with metformin, compared to glimepiride added to current background therapy with metformin.
- To assess change from baseline of urinary albumin to creatinine ratio at Week 52 achieved with saxagliptin, in co-administration with dapagliflozin, added to current background therapy with metformin, compared to glimepiride added to current background therapy with metformin.
- To assess change from baseline of biomarkers (high-sensitivity C-reactive protein [hsCRP], N-terminal pro-brain natriuretic peptide [NT Pro-BNP]) at Week 52 of double-blind treatment achieved with saxagliptin, in co-administration with dapagliflozin, added to current background therapy with metformin, compared to glimepiride added to current background therapy with metformin.

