8.3.3 Exploratory Endpoint(s)

The exploratory endpoints for the short-term treatment period include:

- Proportion of subjects achieving a therapeutic glycemic response, defined as HbA1c < 7.0%, without any hypoglycemia at Week 52.
- Proportion of subjects achieving a therapeutic glycemic response, defined as HbA1c < 7.0%, without any hypoglycemia and weight gain at Week 52.
- Mean change from baseline in FPG at Week 52.
- Mean change from baseline of metabolic measures (glucagon, C-peptide, pro-insulin, insulin, iHOMA2) at Week 52.

- Mean change from baseline in average glucose values and postprandial glucose values measured by 6-point SMBG profiles at Week 52.
- Mean change from baseline in urinary albumin to creatinine ratio at Week 52.
- Mean change from baseline in biomarkers (hsCRP and NT Pro-BNP) at Week 52.
- Mean change from baseline in patient-reported treatment satisfaction, quality of life, and barriers to medication adherence at Week 52.
- In a sub-study: Mean change from baseline in glucose variability, as defined by mean amplitude of glycemic excursions (MAGE), using CGM at Week 52.
- In a sub-study: Mean change from baseline in visceral and subcutaneous adipose tissue volume, and percent hepatic lipid content as assessed by MRI at Week 52 in the subpopulation of subjects who undergo MRI-PDFF.

The exploratory endpoints for the long-term treatment period include:

- Mean change from baseline in HbA1c at Week 156.
- Mean time spent at or below HbA1c target (HbA1c < 7.0%) during 156 weeks.
- Proportion of subjects achieving a therapeutic glycemic response, defined as HbA1c < 7.0%, without any hypoglycemia at Week 156.
- Proportion of subjects achieving a therapeutic glycemic response, defined as HbA1c < 7.0%, without any hypoglycemia and weight gain at Week 156.
- Mean change from baseline in FPG at Week 156.
- Mean change from baseline of metabolic measures (glucagon, C-peptide, pro-insulin, insulin, iHOMA2) at Week 156.
- Mean change from baseline in urinary albumin to creatinine ratio at Week 156.
- Mean change from baseline in biomarkers (hsCRP and NT Pro-BNP) at Week 156.
- Mean change from baseline in total body weight at Week 156.
- Mean change from baseline in systolic blood pressure (SBP) at Week 156.
- Mean change from baseline in patient-reported treatment satisfaction, quality of life, and barriers to medication adherence at Week 156.

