8.4.2.1 Primary Efficacy Analysis

The primary efficacy analysis of HbA1c at Week 52 will be performed using a longitudinal repeated measures model with terms for treatment group, baseline value, time, the interaction of treatment and time, and the interaction of baseline value and time in the model, including observations prior to rescue. Point estimates and 95% confidence intervals will be calculated for the adjusted mean changes within each treatment group, as well as for the differences in adjusted mean changes between treatment groups.

Sensitivity analyses for HbA1c will include additional repeated measures analyses and analysis of covariance (ANCOVA) analyses. The repeated measures analyses will include two separate analyses, including values after rescue, and including and excluding a time-dependent covariate for rescue. Two separate ANCOVA analyses of the change from baseline at Week 52 will be performed, with terms for treatment group and baseline value in the model. One analysis will be based on measurements at Week 52 (if prior to rescue, if applicable) or the last post-baseline measurement prior to Week 52 and prior to rescue (if applicable), if no Week 52 assessment is available (eg, last observation carried forward [LOCF]). The second sensitivity analysis using ANCOVA will be based on all subjects completing the double-blind treatment period without requiring glycemic rescue therapy.

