8.4.2.3 Other Efficacy Analyses

Analyses for other efficacy objectives will use the same methodology for continuous endpoints as described above. For composite response endpoints (glycemic control without hypoglycemia or weight gain), the proportion of subjects achieving targets will be summarized by treatment group without adjustment for baseline. All exploratory endpoints will not be statistically tested.

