7.1.4 Descriptive Summaries of Continuous Variables

Descriptive summaries of continuous variables in terms of change or percent change from baseline values will be provided, including n, mean, median, first quartile (Q1) and third quartile (Q3) and standard error (SE). Geometric mean and coefficient of variation (CV) will be also be provided for lipid panel results. In addition, 95% confidence interval for the mean (percent) change from baseline will be calculated for continuous efficacy variables. They will be presented by treatment group and time point where applicable.

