7.5.8 Biomarker Analyses

The change from baseline in C-Reactive protein and N-Terminal ProB-type Natriuretic Peptide parameters during the short-term and long-term treatment period will be summarized descriptively for each treatment group at week 52 and 156 only.

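### The hsCRP and NT-proBNP objectives are comparisons with glimepiride, but the plan gives only by-arm descriptive summaries and no baseline-adjusted between-arm estimate.

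*Protocol*

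**What the plan says.** **Objective and endpoint.** Protocol 1.3.3 includes the aim "To assess change from baseline of biomarkers (high-sensitivity C-reactive protein [hsCRP], N-terminal pro-brain natriuretic peptide [NT Pro-BNP]) at Week 52", set against glimepiride, and repeats it for Week 156. SAP 3.3 carries both. The endpoint in Protocol 8.3.3 is "Mean change from baseline in biomarkers (hsCRP and NT Pro-BNP) at Week 52", again with a Week 156 counterpart.

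**Analysis of the two markers.** Protocol 8.4.5: "The exploratory biomarker measurements of hsCRP and NT-proBNP will be summarized with descriptive statistics by treatment". SAP 7.5.8 says that the changes "will be summarized descriptively for each treatment group at week 52 and 156 only".

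**Content of a descriptive summary.** SAP 7.1.4 gives n, mean, median, quartiles and standard error of the change or percent change, and a within-arm 95% interval for continuous efficacy variables. It extends to a geometric scale in one case: "Geometric mean and coefficient of variation (CV) will be also be provided for lipid panel results".

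**Treatment of comparable endpoints.** SAP 7.5.5.2 assigns the repeated measures model to FPG and uACR, among others, and ANCOVA to glucagon, C-peptide, pro-insulin, insulin and iHOMA2. Protocol 8.4.6.1 and SAP 7.5.9 give patient-reported outcomes a baseline-adjusted repeated measures model with between-arm differences and intervals. Protocol 8.4.2.3 also has a general rule: "Analyses for other efficacy objectives will use the same methodology for continuous endpoints as described above". The reference is to the model in 8.4.2.1, a "longitudinal repeated measures model with terms for treatment group, baseline value, time, the interaction of treatment and time".

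**The concern.** The objective is a contrast between arms, and the planned output is two separate columns. Two within-arm intervals do not give the interval for the difference, so the plan does not itself produce the quantity that the objective names. Both markers are drawn at Day 1, Week 52 and Week 156, so the baseline needed for a more precise comparison will already be in the database.

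Exploratory status does not explain the gap, because equally exploratory endpoints are modelled. Nor does the statement in Protocol 8.4.2.3 that exploratory endpoints will not be tested: it removes a p-value, not an estimate with an interval. At stake is the precision and usefulness of two exploratory results.

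**Working it through.** **1. The plan's own sample size.** The documents give no figure for the biomarkers. The only stated one (Protocol 8.1, SAP 5) is for HbA1c: difference 0.35, SD 1.1, two-sided alpha 0.05, power 90%, 5% non-evaluable, 220 per arm.

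n = 2 × (1.960 + 1.282)² × 1.1² / 0.35² = 207.6, so 208 per arm. Then 208 / 0.95 = 218.9, so 219, which agrees with 220. Evaluable: 220 × 0.95 = 209 per arm, with power 90.2%. I use 209 per arm below. This is a Week 52 figure for HbA1c; Week 156 may have fewer.

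**2. What a reader could derive.** From n, mean and SE by arm, the difference in mean change has standard error √(SE₁² + SE₂²). It is valid under 1:1 randomization, but unadjusted and on the raw scale.

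**3. Gain from baseline adjustment alone.** With equal variance σ² at both visits and correlation ρ:

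- variance of a change score: 2σ²(1 − ρ)
- residual variance after adjusting for baseline: σ²(1 − ρ²)
- ratio: (1 + ρ) / 2

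At ρ = 0.5 the ratio is 0.75 (a 25% reduction); at ρ = 0.7 it is 0.85 (15%). This needs no assumption about skewness. The correlations are assumed.

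**4. Further gain from a log scale (illustration).** Assumptions: lognormal values, log-scale SD 0.8 to 1.2, ρ 0.5 to 0.7, true ratio 0.80, 209 per arm, 3,000 simulated trials per row. The entries are the share of trials in which the two-sided 5% criterion excludes no difference.

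| Log SD | ρ | Raw change | Log change, unadjusted | Log ANCOVA |
|---|---|---|---|---|
| 0.8 | 0.5 | 58% | 82% | 91% |
| 0.8 | 0.7 | 76% | 96% | 98% |
| 1.0 | 0.5 | 33% | 63% | 77% |
| 1.0 | 0.7 | 47% | 84% | 89% |
| 1.2 | 0.5 | 19% | 47% | 59% |
| 1.2 | 0.7 | 28% | 69% | 76% |

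The ANCOVA column agrees with the closed-form power to within two percentage points. Most of the gain comes from the change of scale, which is the part resting on assumed skewness.

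**5. What the model would report.** The standard error of the log ratio is SD × √(1 − ρ²) × √(2/209).

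- SD 0.8, ρ 0.7: 0.8 × 0.714 × 0.0978 = 0.056; exp(1.96 × 0.056) is about 1.12.
- SD 1.2, ρ 0.5: 1.2 × 0.866 × 0.0978 = 0.102; exp(1.96 × 0.102) is about 1.22.

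The 95% interval would therefore run from the estimated ratio divided by, to the ratio multiplied by, a factor of about 1.12 to 1.22.

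**The case against.** The strongest reply is that the plan is consistent and probably deliberate. Protocol 8.4.5 and SAP 7.5.8 say the same thing, and the amendment history shows that 7.5.8 was added in SAP version 3. A reader might infer from Protocol 8.4.2.3, or from the general ANCOVA text in SAP 7.1.3, that a model is required and the documents contradict themselves. They do not support that. A specific section governs over a general one, biomarkers have their own section outside 8.4.2, and the patient-reported outcomes section shows that the authors wrote out a model where they wanted one. Nor does it help that the SAP lists the markers among efficacy parameters (8.3.1, 8.5, Section 12). Those lists set post-dose cut-offs, lipids appear in them and are also only summarized (7.5.5.3), and SAP 7.6.6 lists the markers with the safety laboratory data.

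It is also fair that medians and quartiles, which resist extreme values, are already planned, that the power figures depend on chosen inputs, and that a multiplicative effect favours the log scale by construction.

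All of this stands. It leaves untouched the mismatch between a comparative objective and an analysis with no comparison, for which neither document gives a reason.

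**Conclusion.** The point holds as a cheap improvement to an exploratory analysis. The objective asks for a comparison, the plan provides none, and the baseline value goes unused as a covariate.

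The firmest part of the size is the 15% to 25% variance reduction from baseline adjustment, given equal variances and a correlation of 0.5 to 0.7. The contrast of 19% to 76% with 59% to 98% illustrates precision under assumed lognormal data; it is not a property of this trial, and no test is planned.

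Two stronger readings are tempting. One is that the plan leaves no usable comparison, or one driven by outliers. That goes too far: a crude difference can be derived, robust summaries are planned, and the documents mention skewness only for uACR. The other is that the missing NT-proBNP contrast weakens the safety assessment, because heart failure leading to hospitalization is a listed potential risk of saxagliptin. The documents do not make NT-proBNP a safety endpoint. They address that risk through blinded adjudication of heart failure hospitalizations and a summary of cardiac failure events.

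Both markers lie outside the testing hierarchy, so no primary or secondary conclusion changes.

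**What to change.** In Protocol 8.4.5 and SAP 7.5.8, keep the descriptive summaries and add text such as:

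> For each of hsCRP and NT-proBNP, at Week 52 and at Week 156, the log-transformed value will be analysed by ANCOVA with treatment group and log baseline value. The between-arm ratio of adjusted geometric means and its 95% confidence interval will be reported as exploratory. No hypothesis test will be performed.

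The model can use the same values and visit windows as the summaries (SAP Tables 8.4 I and J). Reporting an interval without a test is in keeping with Protocol 8.4.2.3. Rewording the objectives as descriptive would also remove the mismatch, but would leave the baseline data unused.

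The cost is one model per marker and visit, four in all, with no new data. The downside is a few more intervals without multiplicity adjustment, to be read with caution. SAP version 3 post-dates the short-term analysis, so a Week 52 model added now should be labelled as added after the sponsor's short-term unblinding.

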8.4.6 Outcomes Research Analyses

8.4.6.1 Patient-reported outcomes (PRO)

Mean change from baseline in patient-reported treatment satisfaction, quality of life, and barriers to medication adherence will be analyzed using longitudinal repeated measures model with terms for treatment group, baseline value, time, the interaction of treatment and time, and the interaction of baseline value and time. Point estimates and 95% confidence intervals will be calculated for the adjusted mean changes within each treatment group as well as for the differences in adjusted mean changes between treatment groups.

8.4.7 Subgroup analysis

Subgroup analyses for age, gender, race, female age, region, and baseline HbA1c category for continuous endpoints will be analyzed as was done for the original analysis, but for the applicable subset of patients. Interaction tests will be performed for time to event and continuous endpoints using the original model with treatment interaction terms added.

8.4.8 Other Analyses

Not applicable

8.5 Interim Analyses

Not applicable

9 STUDY MANAGEMENT

9.1 Compliance

9.1.1 Compliance with the Protocol and Protocol Revisions

The study shall be conducted as described in this approved protocol. All revisions to the protocol must be discussed with, and be prepared by the Sponsor. The investigator should not implement any deviation or change to the protocol without prior review and documented approval/favorable opinion from the IRB/IEC of an amendment, except where necessary to eliminate an immediate hazard(s) to study subjects.

If a deviation or change to a protocol is implemented to eliminate an immediate hazard(s) prior to obtaining IRB/IEC approval/favorable opinion, as soon as possible the deviation or change will be submitted to:

- IRB/IEC for review and approval/favorable opinion
- The Sponsor

- Regulatory Authority(ies), if required by local regulations
- Documentation of approval signed by the chairperson or designee of the IRB(s)/IEC(s) must be sent to the Sponsor

If an amendment substantially alters the study design or increases the potential risk to the subject: (1) the consent form must be revised and submitted to the IRB(s)/IEC(s) for review and approval/favorable opinion; (2) the revised form must be used to obtain consent from subjects currently enrolled in the study if they are affected by the amendment; and (3) the new form must be used to obtain consent from new subjects prior to enrollment.

If the revision is done via an administrative letter, investigators must inform their IRB(s)/IEC(s).

9.1.2 Monitoring

Sponsor representatives will review data centrally to identify potential issues to determine a schedule of on-site visits for targeted review of study records.

Sponsor representatives must be allowed to visit all study site locations periodically to assess the data quality and study integrity. On site they will review study records and directly compare them with source documents, discuss the conduct of the study with the investigator, and verify that the facilities remain acceptable. Certain CRF pages and/or electronic files may serve as the source documents: CGM data, fingerstick blood glucose values recorded in the diary and meter data (SMBGs), and the diary data as noted in [Section 5.3.1](#).

In addition, the study may be evaluated by the Sponsor's internal auditors and government inspectors who must be allowed access to CRFs, source documents, other study files, and study facilities. Audit reports will be kept confidential.

The investigator must notify the Sponsor promptly of any inspections scheduled by Regulatory Authorities, and promptly forward copies of inspection reports to the Sponsor.

9.1.2.1 Source Documentation

The investigator is responsible for ensuring that the source data are accurate, legible, contemporaneous, original and attributable, whether the data are hand-written on paper or entered electronically. If source data are created (first entered), modified, maintained, archived, retrieved, or transmitted electronically via computerized systems (and/or any other kind of electronic devices) as part of regulated clinical trial activities, such systems must be compliant with all applicable laws and regulations governing use of electronic records and/or electronic signatures. Such systems may include, but are not limited to, electronic medical/health records [EMRs/EHRs], adverse event tracking/reporting, protocol required assessments, and/or drug accountability records).

When paper records from such systems are used in place of electronic format to perform regulated activities, such paper records should be certified copies. A certified copy consists of a

copy of original information that has been verified, as indicated by a dated signature, as an exact copy having all of the same attributes and information as the original.

9.1.3 Investigational Site Training

The Sponsor will provide quality investigational staff training prior to study initiation. Training topics will include but are not limited to: GCP, AE reporting, study details and procedure, electronic CRFs, study documentation, informed consent, and enrollment of WOCBP.

9.2 Records

9.2.1 Records Retention

The investigator must retain all study records and source documents for the maximum period required by applicable regulations and guidelines, or institution procedures, or for the period specified by the Sponsor, whichever is longer. The investigator must contact the Sponsor prior to destroying any records associated with the study.

The Sponsor will notify the investigator when the study records are no longer needed.

If the investigator withdraws from the study (eg, relocation, retirement), the records shall be transferred to a mutually agreed upon designee (eg, another investigator, IRB). Notice of such transfer will be given in writing to the Sponsor.

9.2.2 Study Drug Records

It is the responsibility of the investigator to ensure that a current disposition record of study drug (inventoried and dispensed) is maintained at the study site to include IMP and the following non-IMP(s). Records or logs must comply with applicable regulations and guidelines and should include:

- amount received and placed in storage area
- amount currently in storage area
- label identification number or batch number
- amount dispensed to and returned by each subject, including unique subject identifiers
- amount transferred to another area/site for dispensing or storage
- non-study disposition (eg, lost, wasted)
- amount destroyed at study site, if applicable
- amount returned to the Sponsor
- retain samples for bioavailability/bioequivalence, if applicable
- dates and initials of person responsible for IMP dispensing/accountability, as per the Delegation of Authority Form

The Sponsor will provide forms to facilitate inventory control if the investigational site does not have an established system that meets these requirements.

9.2.3 Case Report Forms

An investigator is required to prepare and maintain adequate and accurate case histories designed to record all observations and other data pertinent to the investigation on each individual treated or entered as a control in the investigation. Data that are derived from source documents and reported on the CRF must be consistent with the source documents or the discrepancies must be explained. Additional clinical information may be collected and analyzed in an effort to enhance understanding of product safety. CRFs may be requested for AEs and/or laboratory abnormalities that are reported or identified during the course of the study.

For sites using the Sponsor's electronic data capture tool, electronic CRFs will be prepared for all data collection fields except for fields specific to SAEs and pregnancy, which will be reported on the paper or electronic SAE form and Pregnancy Surveillance form, respectively. Spaces may be left blank only in those circumstances permitted by study-specific CRF completion guidelines provided by the Sponsor.

The confidentiality of records that could identify subjects must be protected, respecting the privacy and confidentiality rules in accordance with the applicable regulatory requirement(s).

The investigator will maintain a signature sheet to document signatures and initials of all persons authorized to make entries and/or corrections on CRFs.

The completed CRF, including any paper or electronic SAE/pregnancy CRFs, must be promptly reviewed, signed, and dated by the investigator or qualified physician who is a sub-investigator and who is delegated this task on the Delegation of Authority Form. For electronic CRFs, review and approval/signature is completed electronically through the Sponsor's electronic data capture tool. The investigator must retain a copy of the CRFs including records of the changes and corrections.

Each individual electronically signing electronic CRFs must meet the Sponsor's training requirements and must only access the Sponsor's electronic data capture tool using the unique user account provided by the Sponsor. User accounts are not to be shared or reassigned to other individuals.

